5.7 Packaging and Labeling

Each packaged unit will be labeled with an investigational label with the information required per applicable regulations.

The products for each study intervention assignment will be packaged into identical randomized intervention kits; each randomized intervention kit will contain one of 2 study interventions: 0.003% AR-15512 ophthalmic solution or AR-15512 ophthalmic solution vehicle.

Additional detail is provided in the Pharmacy Manual.

5.8 Storage

The study intervention must be dispensed and administered according to the procedures prescribed in this protocol and Pharmacy Manual. Only qualified subjects may receive study intervention, in accordance with all the applicable regulatory requirements. Only authorized staff is allowed to dispense these study interventions. Under normal conditions of handling and administration, the study interventions are not expected to pose significant safety risk to site staff. Adequate precautions must be taken to avoid direct contact with the study intervention. The study interventions will be stored in a secure area under the appropriate physical conditions for the product. Access to the study intervention will be limited to authorized site staff only. The study interventions will be stored as directed on the investigational label. The study interventions must be stored in clinic refrigerated (2°C to 8°C/36°F to 46°F) until dispensed to the subject. Temperature of the study intervention storage location at the site is to be monitored using a calibrated monitoring device and documented. Study intervention should be removed from the refrigerator at least 30 minutes before use. At time of dispensing, the subject will be instructed to store the study intervention per details in the Pharmacy Manual and to protect from light (store in carton) as directed on the investigational label. Subjects should be instructed not to freeze the study intervention.

5.9 Accountability

5.9.1 Receipt and Disposition of Study Medication

Study interventions will be shipped to the Investigator's site from a central depot. If a discrepancy is noted, the appropriate individual at the Sponsor or designee must be notified immediately, in accordance with the Pharmacy Manual. The responsible person(s) for dispensing study intervention at the Investigator's site is the only site staff member(s) permitted to distribute study intervention and also has sole responsibility to account for all returned used, partially used and unused vials of study intervention. The study intervention(s) must not be used outside this protocol. An Investigational Product Accountability Log will be kept at each clinical site.

5.9.2 Return of Study Intervention

When the study is completed or is terminated by the Sponsor, all study materials including used and unused study intervention kits / vials will be returned to the Sponsor or their designee. Subjects should be instructed to retain all vials (used, partially used or unused) of study intervention and return them to the clinical site. All study intervention accounting procedures must be completed before the study is considered to be concluded.

The responsible person(s) at the Investigator's site has the sole responsibility to account for all used, partially used, and unused study intervention. This site staff member at the Investigator's site will complete a study intervention returns form or equivalent that will be signed by the Investigator or designee prior to returning the used and unused study intervention vials to the Sponsor or their designee.

6. STUDY PROCEDURES

6.1 Informed Consent

Prior to any study procedures, the study will be discussed with each subject, and subjects wishing to participate must give written informed consent. The verbal explanation of the study will cover all the elements specified in the written information provided for the subject. The Investigator will inform the subject of the aims, methods, anticipated benefits, and potential hazards of the study, including any discomfort it may entail. The subject must be given every opportunity to clarify any points he/she does not understand and, if necessary, may ask for more information. At the end of the interview, the subject should be given time to reflect. Subjects and/or a legally authorized representative then will be required to sign and date the ICF.

The ICF must have received approval/favorable review by a properly constituted Institutional Review Board (IRB) prior to use. A copy of the signed and dated consent document will be given to each subject. The original signed and dated ICF must be maintained in the study files at the Investigator's site.

The Investigator or staff is responsible for ensuring that no subject is exposed to any study related examination or activity before the subject has given written informed consent. It should be emphasized that the subject is at liberty to withdraw consent to participate at any time, without penalty or loss of benefits to which the subject is otherwise entitled. Subjects who refuse to give, or withdraw, written informed consent may not be included or continued in this study, and should be notified that discontinuation from the study will not impact their subsequent care.

6.2 Demographics, Medical and Surgical History

Demographic data will be collected and recorded. Significant medical and ophthalmic history will be collected and any current underlying medical/ophthalmic conditions, including those that may have resolved before the Screening visit, must also be recorded. All relevant medical and ophthalmic surgical procedures should be recorded.

6.3 Prior and Concomitant Medication Assessments

Any medication (including vaccines, OTC, prescription medicines, vitamins, and/or herbal supplements) that the participant is receiving at the time of enrollment or receives during the study must be recorded. Prior medications taken up to at least 90 days prior to the Screening visit must also be recorded. Additional details on prohibited and allowable medications can be found in the Supplemental Medication Guide.

6.4 Clinical Laboratory Tests

6.4.1 Laboratory Parameters

A chemistry panel, a complete blood count (hematology and differential), and urinalysis will be performed as described in the Laboratory Manual.

6.4.2 Sample Collection, Storage and Shipping

The site staff responsible for collecting the laboratory samples will be identified on the Site Authorization and Delegation Log. Details for the preparation and shipment of samples and reference ranges will be provided in the Laboratory Manual.

6.4.3 Pregnancy Testing

Urine pregnancy tests for women of childbearing potential (WOCBP; defined in Section 4.5.4) are required at Screening, Baseline and Day 90 (Study Exit) visits. Pregnancy tests must be negative for the subject to receive study intervention.

6.5 Dispensing Study Intervention

Masked study-related site personnel will be cautioned that any used or unused study intervention kits are not to be opened at the clinical site by the site staff involved in efficacy or safety assessments.

Study staff responsible for dispensing study intervention will be listed on the Site Authorization and Delegation Log. When a subject meets all criteria for enrollment, the subject will be randomly assigned to a study intervention according to the IRT. The responsible study staff will account for all used, partially used and unused study kits / vials by maintaining a Study Intervention Accountability log.

See Table 3 for the study intervention dispensing schedule. Details of timing and procedures for dispensing study intervention are found in the Pharmacy Manual.

Table 3 Study Intervention Dispensing Schedule

Study Day	Quantity Dispensed to Subject
-14	1 Run-In kit (40 vials)
1	1 Randomized Intervention Kit (40 vials)
7	1 vial administered in-office from the Day 7 Kit
14	1 Randomized Intervention Kit (40 vials)
28	2 Randomized Intervention Kits (80 vials)
60 ¹	2 Randomized Intervention Kits (80 vials)
90	Study Exit

¹ Dispensation and collection of study intervention only. No other procedures are scheduled on this day.

6.6 Efficacy Assessments

6.6.1 Symptom Questionnaire (Visual Analog Scale (VAS))

Subjects will be asked to rate each of the following DED symptoms (both eyes together), over the last 24 hours, each on a separate VAS: *ocular discomfort (ODS)*, *eye dryness (EDS)*, [REDACTED] For each VAS, subjects will be asked to place a vertical mark on the horizontal line to indicate the level of each symptom, with 0 corresponding to “no symptom” and 100 corresponding to “maximal symptom”. The assessment line length of each scale will be 100 mm (Figure 2). Instructions for measuring each subject’s response on each VAS can be found in the Manual of Procedures.

Figure 2 Ocular Discomfort: Visual Analog Scale

Eye Dryness: Visual Analog Scale

6.6.2 Symptom Assessment in Dry Eye Questionnaire

The SANDE questionnaire ([Schaumberg 2007](#)) is comprised of 2 unique VASs to assess the frequency and severity of DED symptoms. Subjects will be asked to complete the SANDE to rate both the frequency and severity of DED symptoms for both eyes together. Each of the two questions will be accompanied by a VAS. The assessment line length of the scale will be 100 mm and will be similar to the following depiction (Figure 3). Higher scores indicate greater frequency or severity.

Instructions for measuring each subject's response on each VAS can be found in the Manual of Procedures. The SANDE score will be calculated by multiplying the frequency score by the severity score and obtaining the square root. The final value must be rounded to the nearest whole number.

Figure 3 SANDE Questionnaire

PLEASE COMPLETE THE FOLLOWING QUESTIONS REGARDING THE FREQUENCY AND SEVERITY OF YOUR DRY EYE SYMPTOMS:

1. Frequency of symptoms:

[figure not shown]
Place a single vertical mark on the horizontal line to indicate how often, on average, your eyes feel dry and/or irritated.

2. Severity of symptoms:

Place a single vertical mark on the horizontal line to indicate how severe, on average, you feel your symptoms of dryness and/or irritation.

[figure not shown]

[figure not shown]
6.6.7 Unanesthetized Schirmer Test

[figure not shown]
Two unanesthetized Schirmer tests will be performed on both eyes at each of the Baseline (Day 1), Day 7, Day 14, Day 28 and Day 90 visits.

[figure not shown]
Placement and removal of the strips should be performed by the Investigator, sub-Investigator or designated trained personnel. Reading of the strips post-test, should be performed by only the Investigator or sub-Investigator. Every effort should be made to ensure the same individual(s) performs this assessment for a given subject at each applicable visit.

Additional details can be found in the Manual of Procedures.

6.7.2 Controlled Adverse Environment Exposure

Subjects will be exposed to the CAE for approximately 90 minutes during the Screening visit.

6.8 Safety Assessments

6.8.1 Vital Signs

Systolic and diastolic blood pressure will be measured using an appropriate sphygmomanometer after subjects have been at rest (seated) for at least 5 minutes. Blood pressure will be recorded in mmHg.

Heart rate will be measured using manual or automated methods in beats per minute (bpm) after the subject has been in a resting state (seated) for at least 5 minutes. If measured manually, pulse will be counted for 30 seconds, multiplied by 2, and recorded in beats per minute.

6.8.2 Corrected Visual Acuity

Logarithmic minimum angle of resolution (LogMAR) visual acuity in both eyes must be assessed using an ETDRS Series 2000 chart. Visual acuity should be evaluated prior to ocular examinations as specified in the Schedule of Visits and Procedures ([Appendix 1](#)). Additional procedural details can be found in the Manual of Procedures.

6.8.3 Biomicroscopy

Slit lamp biomicroscopic observations will be graded as Normal or Abnormal. Abnormal findings will be categorized as clinically significant (findings that may interfere with study parameters or otherwise confound the data as determined by the investigator) or not clinically significant (NCS). The following will be examined in both eyes:

- Cornea
- Conjunctiva
- Anterior Chamber

- Iris
- Lens
- Eyelid

Additional procedural details can be found in the Manual of Procedures.

6.8.4 Intraocular Pressure

The IOP must be measured in both eyes only after the biomicroscopic exam is completed and must be measured prior to pupil dilation. IOP will be taken by qualified study site personnel with the subject seated. Every effort should be made to ensure that the same study site personnel use the same device for IOP measurement for a given subject. A Goldmann applanation tonometer affixed to a slit lamp is the preferred device for IOP measurement.

6.8.5 Dilated Fundoscopy

Dilated fundus exams will be performed in both eyes using indirect ophthalmoscopy. The Investigator will make observations of the vitreous, retina, macula, choroid and optic nerve.

Observations will be graded as Normal or Abnormal. Abnormal findings that are clinically significant (as determined by the Investigator that may interfere with study parameters or otherwise confound the data) and those that are not clinically significant will be described. An indirect Fundoscopy examination should be performed if retinal disease is detected.

- Vitreous: Examination should emphasize the visual axis.
- Retina, Macula, Choroid: Include an observation of the retina and its blood vessels. Eyes should be excluded from the study if active inflammation is present.
- Optic Nerve: Significant damage or cupping to the optic nerve should be noted.

It is recommended that tropicamide 1% ophthalmic solution be used to dilate subjects.

6.9 Adverse Events Assessments

6.9.1 Performing Adverse Event Assessments

All AEs occurring during the study, regardless of the assumption of causal relationship, must be documented on the respective eCRF.

Qualified study staff responsible for assessing AEs will be listed on the Site Authorization and Delegation Log. This includes assessment of AE severity and relationship to treatment. AE information may be volunteered by the subject or solicited by study personnel through non-leading questions.

Documentation of AEs/adverse reactions will include AE description, start date and stop date, severity, relationship, action(s) taken, seriousness, and outcome.

If a disease is known at the time an AE is reported, this diagnosis should be recorded rather than listing of individual symptoms. However, if a cluster of symptoms cannot be identified as a single diagnosis, each individual event should be reported separately. If a diagnosis is subsequently known, it should be reported as follow-up information.

When recording an AE, the following information should be provided on the study AE eCRF:

1. Action Taken with Study Intervention:
 - None
 - Study Intervention Discontinued
 - Study Intervention Interrupted
2. AE Outcome:
 - Fatal
 - Not Recovered/Not Resolved
 - Recovered/Resolved
 - Recovered/Resolved with sequelae
 - Recovering/Resolving
 - Unknown/Lost to follow-up

6.9.2 Adverse Event Definitions

The following definitions of terms apply to this section:

- Adverse event (AE): any untoward medical occurrence associated with the administration of the study intervention in humans, whether or not considered to be related to the study intervention.
- Adverse reaction (AR): any AE for which there is a reasonable possibility that the administration of the drug caused the AE. For the purposes of Investigational New Drug (IND) safety reporting, “reasonable possibility” means there is evidence to suggest a causal relationship between the administration of the drug and the AE. See Section [6.9.5](#).
- Life-threatening AE or life-threatening AR: an AE or AR is considered “life-threatening” if, in the view of either the Investigator or Sponsor, its occurrence places the subject at immediate risk of death. It does not include an AE or AR that, had it occurred in a more severe form, might have caused death.
- Serious adverse event (SAE) or serious adverse reaction (SAR): an AE or AR is considered “serious” if, in the view of either the Investigator or Sponsor, it results in any of the following outcomes: Death, a life-threatening or sight-threatening AE, subject hospitalization or prolongation of existing hospitalization, a persistent or significant incapacity or substantial disruption of the ability to conduct normal life functions, or a congenital anomaly/birth defect. Important medical events that may not result in death,

be life-threatening, or require hospitalization may be considered serious when, based upon appropriate medical judgment, they may jeopardize the subject and may require medical or surgical intervention to prevent one of the outcomes listed in this definition. Examples of such medical events include allergic bronchospasm requiring intensive treatment in an emergency room or at home, blood dyscrasias, or convulsions that do not result in subject hospitalization, or the development of drug dependency or drug abuse. Neither the condition, hospitalization, prolonged hospitalization, nor surgery are reported as a serious adverse event when the hospitalization or prolonged hospitalization was for an elective surgical procedure or for a preexisting condition (with no increase in severity).

- Unexpected AE or unexpected AR: an AE or AR is considered “unexpected” if it is not listed in the Investigator’s Brochure or is not listed at the specificity or severity that has been observed; or, if an Investigator’s Brochure is not required or available, is not consistent with the risk information described in the general investigational plan or elsewhere in the current application, as amended. See Section [6.9.6](#).

6.9.3 Reporting Adverse Events

AEs should be documented from the time the subject provides informed consent until subject participation in the study has been completed. If a serious or non-serious AE or adverse reaction is unresolved at the time of exit, efforts will be made to follow up until the AE or adverse reaction is resolved or stabilized, the subject is lost to follow-up, or there is other resolution to the event. These follow-up visits will be documented.

If an event occurs after informed consent but prior to subject enrollment and the commencement of study medication, it should be recorded as an AE. Any change in the health status after commencement of study medication should be recorded as treatment emergent adverse events (TEAEs).

Surgery should not be reported as an outcome of an adverse event if the purpose of the surgery was diagnostic and the outcome was uneventful.

6.9.3.1 AEs and Prior Medical History

Any medical condition present prior to informed consent which remains unchanged or improved should not be recorded as an AE at subsequent visits. However, an AE should be recorded if the frequency, intensity, or the character of a pre-existing condition worsens during the study period beyond what would be expected from the natural progression of that condition.

Symptoms and signs that are consistent with the natural history of DED are not considered reportable adverse events. Such developments are recorded but are not reportable adverse events. Worsening of symptoms and signs of DED should be recorded as an AE or SAE only if judged by the investigator to have unexpectedly worsened in severity and/or frequency or

changed in nature at any time during the study. When recording an unanticipated worsening of DED, it is important to convey why the development was unexpected.

If there is a question as to whether a medical development should be reported as an adverse event, the Investigator is recommended to contact the Sponsor for guidance.

6.9.4 Severity

Severity of an AE is defined as a qualitative assessment of the level of discomfort or the degree of intensity of an AE as determined by the Investigator or reported to them by the subject. The assessment of severity is made irrespective of study medication relationship or seriousness of the event and should be evaluated according to the following scale:

- 1 = Mild: present and noticeable, but not distressing, and no disruption of normal daily activities
- 2 = Moderate: bothersome, discomfort sufficient to possibly reduce or affect normal daily activity
- 3 = Severe: incapacitating, with inability to work or perform normal daily activity

A change in increased severity for a reported AE will require a stop date for the previous severity and a new start and stop date for the new severity. For example, a change in severity may go from mild to moderate, or from moderate to severe. In either case, the start and stop dates should be recorded.

Note: A severe AE is not the same as a serious AE. Seriousness of an AE (NOT severity) serves as a guide for defining regulatory reporting obligations (see Section [6.9.8](#) for further information on SAEs, SARs, and suspected unexpected serious adverse reactions [SUSARs]).

6.9.5 Relationship

A relationship between the AE and the study intervention or study procedure will be determined by the Investigator, as applicable, for each AE using these explanations:

- Not Related: The event is clearly related to other factors such as subject's clinical condition, therapeutic interventions, concomitant disease, or therapy administered to the subject and does not follow a known response pattern to the product, device, or procedure.
- Unlikely Related: The event is most probably caused by other etiologies such as subject's underlying condition, therapeutic intervention, or concomitant therapy; or the delay between administration and the onset of the AE is incompatible with a causal relationship. Therefore, there is not a reasonable possibility that the AE was caused by the product, device, or procedure.

- Possibly Related: The event follows a reasonable, temporal sequence from the time of study medication administration or study procedure and/or follows a known response pattern to the product, device or procedure but could have been produced by other factors such as the subject's clinical state, therapeutic interventions, or concomitant therapy administered to the subject.
- Related: The event follows a reasonable, temporal sequence from the time of study medication administration or study procedure and/or follows a known response pattern to the product, device or procedure and cannot be reasonably explained by other factors such as subject's clinical state, therapeutic interventions or concomitant therapy administered to the subject, and either occurs immediately following study medication administration or procedure, or improves on stopping the study medication, or reappears on repeat exposure, or there is a positive reaction at the application site.

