14.1 Adverse Events

An AE is defined as any untoward medical occurrence associated with the administration of the study intervention in humans, whether or not considered to be related to the study intervention. Any medical condition present prior to informed consent which remains unchanged or improved should not be recorded as an AE at subsequent visits. Any pre-existing medical condition that worsens after first administration of the study intervention will also be considered a new AE. AEs should be documented from the time the subject provides informed consent until subject participation in the study has been completed. All AEs will be coded using MedDRA Version 25.0.

Treatment-emergent adverse events (TEAEs) are defined as any event that occurs or worsens on or after the day that randomized study intervention is initiated. Only TEAEs will be included in the summary tables by treatment group, but all AEs will be included in the subject listings.

Severity of an AE (mild, moderate, and severe) is defined as a qualitative assessment of the degree of intensity of an AE as determined by the Investigator or reported to him/her by the subject. The relationship of each AE (not related, unlikely related, possibly related, and related) to the study intervention and the expectedness of each AE (unexpected and expected) should be determined by the Investigator.

An overall summary will be presented that includes the number of events and the number and percentage of subjects who experienced at least one event for the following: TEAEs, serious TEAEs, serious TEAEs related to study intervention. TEAEs related to study intervention include possibly related or related TEAEs. TEAEs will also be classified by strongest relationship to study intervention (not related, unlikely related, possibly related, or related) and by maximum severity (mild, moderate, or severe). The number of events and number and percentage of subjects with a TEAE leading to study intervention discontinuation and with a TEAE leading to death will also be summarized. In addition, similar overall summaries for ocular TEAEs and non-ocular TEAEs will be presented.

[figure not shown]

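### The causality scale merges drug and study procedure, while the SAP tabulates its top two levels as related to study intervention

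*Protocol*

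**What the plan says.** Protocol 6.9.5 opens by stating what is rated: "A relationship between the AE and the study intervention or study procedure will be determined by the Investigator, as applicable, for each AE". One set of four definitions follows: Not Related, Unlikely Related, Possibly Related and Related. Each names the product (or study medication) and the procedure together.

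- Not Related requires, among other things, that the event "does not follow a known response pattern to the product, device, or procedure".
- Unlikely Related ends: "Therefore, there is not a reasonable possibility that the AE was caused by the product, device, or procedure".
- Possibly Related is met by an event that "follows a known response pattern to the product, device or procedure but could have been produced by other factors".
- Related accepts, as one of its supporting features, that the event "either occurs immediately following study medication administration or procedure".

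Protocol 6.9.1 lists what is documented for each AE after its description: "start date and stop date, severity, relationship, action(s) taken, seriousness, and outcome". Relationship appears once, with no qualifier. Protocol 6.9.2 defines an adverse reaction as "any AE for which there is a reasonable possibility that the administration of the drug caused the AE" and refers the reader to 6.9.5 for that judgement.

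SAP 14.1 takes over the four levels, describes them as relationship to the study intervention, and sets the counting rule: "TEAEs related to study intervention include possibly related or related TEAEs". The outputs that use attribution are Tables 14.3.1.3.1 and 14.3.1.3.2 (treatment-related TEAEs), Tables 14.3.1.7.1 and 14.3.1.7.2 (strongest relationship), and the count of related serious TEAEs in the overall summary.

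**The concern.** The scale asks whether drug or procedure could have caused the event. The table titles say that the answer concerns the drug alone. The visible SAP has no step that removes procedure-caused events before the related counts are formed.

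The trial exposes every subject to repeated ocular procedures that could produce such events. In each completer the unanesthetized Schirmer test alone is done twice, in both eyes, at five visits. The post-drop test follows in-office dosing of the same eye, so timing alone may not tell the investigator which of the two caused a reaction.

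At stake is whether the treatment-related tables measure what their titles say. These are descriptive safety outputs. No efficacy endpoint is touched.

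**Working it through.** The plan states no figure on this point, so the main check is a comparison of texts.

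**Step 1. Apply each level to an event plainly caused by a study procedure** (for example, irritation from a test strip), assuming one rating per event and a literal reading.

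| Level (Protocol 6.9.5) | Requirement that decides the case | Met? |
|---|---|---|
| Not Related | No known response pattern to product, device or procedure | No |
| Unlikely Related | No reasonable possibility that product, device or procedure was the cause | No |
| Possibly Related | Plausible timing and/or a known response pattern to product, device or procedure, with other factors possible | Yes |
| Related | As above, no other reasonable explanation, and (as one option) onset right after dosing or procedure | Yes, if those hold |

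At no level is a study procedure listed among the other factors that point away from relatedness.

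**Step 2. Carry the rating into the SAP.** Under SAP 14.1, Possibly Related and Related both count as related to study intervention, so the event in Step 1 is counted.

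**Step 3. Check the time window.** SAP 14.1 starts the TEAE window on the day randomized intervention is initiated. Reactions to Screening procedures therefore stay out of the summary tables. All Day 1 procedures fall inside the window, including the pre-drop Schirmer test, which Protocol 7.2.1 lists before the first randomized dose.

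**Step 4. Count the opportunities.** From Protocol 6.6.7 and Appendix 1: 2 tests × 2 eyes × 5 visits = 20 strips per completer, plus tonometry, dilation and laboratory sampling on Days 1 and 90. This shows exposure. It says nothing about how often an AE results.

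**Step 5. Direction and shape of the effect (illustration only).** The rates here are assumptions with no source in the documents. Let p be the true drug-related rate in an arm and q the rate of procedure-caused TEAEs, equal in both arms and independent of drug reactions. The tabulated related rate is 1 − (1 − p)(1 − q). The difference between arms becomes (p₁ − p₀)(1 − q). Take p₁ = 15% and p₀ = 5%, which gives a ratio of 3.0 and a difference of 10.0 points.

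| q | AR-15512 | Vehicle | Ratio | Difference (points) |
|---|---|---|---|---|
| 2% | 1 − 0.85 × 0.98 = 16.7% | 1 − 0.95 × 0.98 = 6.9% | 2.4 | 9.8 |
| 5% | 1 − 0.85 × 0.95 = 19.25% | 1 − 0.95 × 0.95 = 9.75% | 2.0 | 9.5 |
| 10% | 1 − 0.85 × 0.90 = 23.5% | 1 − 0.95 × 0.90 = 14.5% | 1.6 | 9.0 |

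Both absolute rates rise and the ratio moves toward 1. The difference shrinks only by the fraction q.

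**The case against.** The strongest reply is that the rating is meant to be drug-specific. The words *as applicable* in 6.9.5 can be read as applying one set of definitions to whichever relationship is being judged. A strip reaction would then be Related to the procedure and Not Related to the drug. Protocol 6.9.1 speaks of relationship to treatment, 6.9.2 of causation by the drug, and SAP 14.1 of the study intervention. The AE eCRF page is not in the documents, and one word in a list of documentation items is not a form specification. The SAP table list also has a gap after Table 14.3.1.7.2 that may be redaction, so a procedure-related table may exist unseen.

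This stands in part. A reader might infer that a procedure reaction can only be rated Possibly Related or Related. The documents do not settle that: it follows only from a literal reading with a single rating. But if two ratings do exist, the visible SAP does not say which one feeds the tables. A further table that is not visible would not by itself remove these events from the visible ones.

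A reader might also infer that a serious procedure-caused event would be reported as a reaction to the drug. The documents do not support this. Protocol 6.9.8.1 requires the SAE form to assess separately whether the drug caused the event, and the Medical Monitor evaluates the reports. Only the SAP's count of related serious TEAEs is exposed.

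Finally, the consequence is limited. The AE summaries are descriptive, the all-TEAE, ocular and non-ocular tables (14.3.1.2.1 to 14.3.1.2.3) do not use attribution, and both arms follow the same procedures on the same schedule. All of that is correct.

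**Conclusion.** The point holds as an inconsistency to be reconciled. Protocol 6.9.5 does not separate drug from procedure causality, Protocol 6.9.2 relies on it for a drug-only definition, and SAP 14.1 tabulates its top two levels as drug-related. Followed literally with one rating per AE, the stated rule misclassifies procedure-caused TEAEs in Tables 14.3.1.3.x and 14.3.1.7.x and in the related serious TEAE count.

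The expected effect is a higher absolute related rate in both arms and a ratio closer to 1. The size cannot be derived, because the documents give no procedure-event rate and do not show the eCRF. It would be too strong to say that a drug effect would be hidden: with an equal, independent background the absolute difference is nearly preserved. The conclusion rests on the single-rating reading and on the visible SAP text.

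**What to change.** 1. **Protocol 6.9.5:** define the rating to study intervention without the references to device and procedure. Record relationship to study procedure as a separate item if the AE eCRF does not already do so.
2. **SAP 14.1:** state that the treatment-related tables, the relationship tables and the related serious TEAE count use the study-intervention rating only. List procedure-related TEAEs separately.
3. **Before unmasking:** query AEs already rated Possibly Related or Related where the rating does not show whether drug or procedure was meant.

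The cost is protocol and SAP wording, at most one extra eCRF item, and a limited set of masked queries. No additional subjects, visits or procedures are needed.
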